10. APPENDICES

Appendix 1. DATA DERIVATION DETAILS

Appendix 1.1. Definition and Use of Analysis Windows in Reporting

The MMRM models for circulating biomarkers and cognitive assessments, and summaries of safety variables (including depression assessments) will require the assignment of observations to scheduled visits, i.e., analysis windows. Safety summaries and analyses will use a different set of windows than summaries and analyses of circulating biomarkers. For safety analyses, the windows will be based on the subject's date of first dose on randomized study medication; the first day of dosing is Day 1. For other summaries and analyses, the day of randomization is Day 1. For both safety and efficacy analyses, if two or more measurements fall in an analysis window, the measurement closest to the target day will be used.

The following table contains the analysis windows for circulating biomarkers and outcomes research variables.

Table 3. Analysis Windows for Circulating Biomarkers and PK/PD

Visit Label	Target Day	Randomization Days*
Visit 6: Week 4 (Month 1)	29	19-39
Visit 7: Week 8 (Month 2)	57	47-67
Visit 8: Week 14 (Month 3)	99	89-109
Visit 9: Week 26 (Month 6)	183	153-213
Visit 10: Week 40 (Month 9)	281	251-311
Visit 11: Week 52 (Month 12)	365	335-395
Visit 12: Week 70 (Month 16)	491	461-521
Visit 13: Week 86 (Month 20)	603	573-633
Visit 14: Week 104 (Month 24)	729	699-759
Visit 15: Week 122 (Month 28)	855	825-885
Visit 16: Week 140 (Month 32)	[contact]
Visit 17: Week 156 (Month 36)	1093	1063-1123
Visit 18: Week 174 (Month 40)	1219	1189-1249
Visit 19: Week 192 (Month 44)	1345	1315-1375
Visit 20: Week 208 (Month 48)	1457	1427-1487

*Randomization days = measurement date – Day 1 (randomization date) + 1

The safety windows will touch, so that all post-baseline safety observations will fall in a window. The following table contains the windows for safety analyses.

Table 4. Analysis Windows for Safety Including Cognitive Assessments

Visit Label	Target Day	Study Days*
Visit 6: Week 4 (Month 1)	29	2-42
Visit 7: Week 8 (Month 2)	57	43-77
Visit 8: Week 14 (Month 3)	99	78-140
Visit 9: Week 26 (Month 6)	183	141-231
Visit 10: Week 40 (Month 9)	281	232-322
Visit 11: Week 52 (Month 12)	365	323-427
Visit 12: Week 70 (Month 16)	491	428-546
Visit 13: Week 86 (Month 20)	603	547-665
Visit 14: Week 104 (Month 24)	729	666-791
Visit 15: Week 122 (Month 28)	855	792-917
Visit 16: Week 140 (Month 32)	[contact]
Visit 17: Week 156 (Month 36)	1093	1037-1155
Visit 18: Week 174 (Month 40)	1219	1156-1281
Visit 19: Week 192 (Month 44)	1345	1282-1400
Visit 20: Week 208 (Month 48)	1457	1401-Open ended

* Study days = measurement date – Day 1 (date of first dose of randomized study medication) + 1

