**Lipid, ADA, PK, and PCSK9 testing requirements after randomization:**

Lipid (direct LDL-C and lipid panel), ADA, PK, and PCSK9 testing, after randomization, when required, should be scheduled **no sooner than 10 days after the subject's prior dose**, even if this requires an unscheduled visit. If a subject has a visit that is scheduled less than 10 days after the last dose, the visit procedures may take place, but lipid, ADA, PK, and PCSK9 testing should be postponed and performed at the earliest possible time, at an unscheduled visit, no sooner than 10 days after the subject's last dose. A lipid profile will not be collected at EDC/EOS visits. ADA, PK, and PCSK9 samples will be collected at EDC/EOS visits.

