*Lipid (direct LDL-C and lipid panel), ADA, PK, and PCSK9 testing, after randomization, when required, should be scheduled **no sooner than 10 days after the subject's prior dose**, even if this requires an unscheduled visit. If a subject has a visit that is scheduled less than 10 days after the last dose, the visit procedures may take place, but lipid, ADA, PK, and PCSK9 testing should be postponed and performed at the earliest possible time, at an unscheduled visit, no sooner than 10 days after the subject's last dose. A lipid profile will not be collected at EDC/EOS visits. ADA, PK, and PCSK9 samples will be collected at EDC/EOS visits.*

Visit windows:

The run-in period is of up to 6 weeks duration, starting at Visit 2, so that there is some flexibility for scheduling the subjects. The run-in visits should take place no less than 7 and no more than 14 days apart. The run-in period continues until Visit 5, randomization. Visit 5 should be scheduled no more than 14 days after Visit 4, the final run-in visit.

After Visit 5, all visits will have a visit window ± 14 days, except for Visits 8 (the Week 14 visit), 11 (the Week 52 visit), both which will have visit window of ± 3 days, and EDC/EOS visits, which will not have visit windows. It will be important to ascertain that the lipid level testing requirement stated above, is met.

Dosing windows:

After randomization, investigational product dosing windows are 1 day before or up to 4 days after the scheduled dosing date. If more than 4 days after the scheduled day have passed, the subject should skip the dose and resume dosing following the dosing schedule provided by site personnel for the next injection.

***Visit 2, start of run-in:** Run-in Visit 2 can occur up to 14 days after Visit 1, depending upon the availability of Visit 1 lab results, additional medical records, if they are needed, and the schedule of the subject and clinical site. At Run-in Visit 2, the initiation of the run-in period, the subject will be shown how to self-inject investigational product (placebo). Only during the run-in period (Visits 2, 3, and 4), subjects will be seen up to two weeks apart, to ascertain the subjects' ability to self-inject investigational product. The other run-in procedures specified in this Schedule of Activities will be adhered to.*

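### SAP Table 3 leaves some allowed Week 4 and Week 8 lipid draws without an analysis window, and a postponed Week 14 draw can just miss its window

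*SAP*

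**What the plan says.** **Analysis windows.** SAP Appendix 1.1 counts the day of randomization as Day 1 for everything except safety. Its Table 3 ("The following table contains the analysis windows for circulating biomarkers and outcomes research variables") gives "Visit 6: Week 4 (Month 1) 29 19-39" and "Visit 7: Week 8 (Month 2) 57 47-67", meaning target days 29 and 57 with ±10 days each. Week 14 has target Day 99 and window Days 89-109. The next window, Week 26, opens on Day 153. If several values fall in one window, the one nearest the target is used. No rule covers a value that falls between windows.

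**Where Table 3 is used.** SAP 8.2.2 assigns observations to visits through Table 3 for the biomarker MMRM, and SAP 8.2.4.3 uses it for the LDL-C response summaries by antibody status. The ANCOVA of LDL-C at the last post-baseline value is stated in SAP 8.2.2 to use no windows.

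**Allowed visit days.** The Schedule of Activities, repeated in SAP Appendix 2, says "After Visit 5, all visits will have a visit window ± 14 days, except for Visits 8 (the Week 14 visit" and Visit 11 (Week 52), "both which will have visit window of ± 3 days".

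**Draw timing.** When a post-randomization visit falls fewer than 10 days after the last dose, the protocol says "lipid, ADA, PK, and PCSK9 testing should be postponed and performed at the earliest possible time, at an unscheduled visit, no sooner than 10 days", counted from that dose.

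**Contrast.** For the safety windows in Table 4 the SAP says "The safety windows will touch, so that all post-baseline safety observations will fall in a window". It says nothing of the kind for Table 3.

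**The concern.** Two parts of the plan disagree about which days count. A site can see a subject on a day that the protocol permits, draw the lipids as instructed, and produce a value that the MMRM cannot use because no Table 3 row contains that day.

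The Week 14 issue is different. The Table 3 window there is wider than the visit window, so the visits are safe. The draw, however, can be moved away from the visit. Day 99 is a nominal dosing day under two-weekly dosing, and Day 99 plus 10 is Day 109, the last day of the window. A subject who injects shortly before the visit and is sent back for blood can therefore be drawn just outside it.

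At stake are the precision and completeness of the by-visit lipid estimates. Week 14 matters most because it is the named time point for LDL-C and the lipid panel. Samples taken at the end of the dosing interval are the ones the protocol brings subjects back to provide, and whether they count would depend on injection and visit timing.

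**Working it through.** **Inputs.** Table 3 and day numbering: SAP Appendix 1.1. Visit windows (±14 days; ±3 at Weeks 14 and 52), 10-day rule and dosing window (1 day early to 4 days late): protocol Schedule of Activities. Dosing every 14 days: protocol 5.1.5, giving nominal dose days 1, 15, 29, 43, 57, 71, 85, 99, 113.

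**Step 1: reproduce the target days.** Target = 7 × week + 1. Week 4: 7 × 4 + 1 = 29. Week 8: 57. Week 14: 99. The formula returns all 14 legible targets in Table 3 (the Visit 16 row is masked).

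**Step 2: compare allowed visit days with Table 3.**

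| Visit | Allowed days | Table 3 | Allowed days in no window |
|---|---|---|---|
| Week 4 | 29 ± 14 = 15-43 | 19-39 | 15-18, 40-43 (8 of 29) |
| Week 8 | 57 ± 14 = 43-71 | 47-67 | 43-46, 68-71 (8 of 29) |
| Week 14 | 99 ± 3 = 96-102 | 89-109 | none (0 of 7) |
| Later legible visits | ±14 (Week 52: ±3) | ±30 | none |

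Day 43 is shared by Weeks 4 and 8, so over Days 15-71 the gap is 8 + 8 - 1 = 15 of 57 days.

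**Step 3: add the 10-day rule at Weeks 4 and 8.** With doses exactly on the nominal days and samples taken before dosing, draws are possible on Days 15, 25-29 and 39-43 for Week 4, and on Days 43, 53-57 and 67-71 for Week 8. Outside the windows are 15 and 40-43 (5 of 11), and 43 and 68-71 (5 of 11). A Day 16-18 visit after a Day-15 dose is drawn on Day 25, which is inside. If the Day-15 dose is still to come, a Day 16-18 draw is permitted and has no window.

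**Step 4: Week 14 postponed draws.** I enumerated visit Days 96-102 (7), the Day-85 dose taken on Days 84-89 (6) and the Day-99 dose taken on Days 98-103 (6): 7 × 6 × 6 = 252 combinations. A dose on the visit day is given after the procedures. Earliest postponed draw = last dose + 10.

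- 96 combinations need postponement.
- In 78 the earliest draw is on or before Day 109 and is kept.
- In 18 it is outside: dose Day 100 with visit Day 101 or 102 (100 + 10 = Day 110), or dose Day 101 with visit Day 102 (101 + 10 = Day 111).
- Dose Day 99 with visit Days 100-102 gives 99 + 10 = Day 109. This is kept, but a one-day slip loses it.
- Days 110-152 are in no window.

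These are unweighted scenarios, not expected frequencies.

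**Step 5: illustrations under assumed timing.** The documents give no distribution of visit or dose days, so every input here is an assumption.

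- Weeks 4 and 8, visit day normal about the target and truncated at ±14: the share of visits on a gap day is 0.8%, 3% or 10% for SD 4, 5 or 7 days, and 8/29 = 28% if uniform. Applying the 10-day rule with exactly nominal dosing gives 0.4%, 1.8% or 5.8%, and 5/29 = 17%.
- With visit SD 5, variable dose days and 10% to 50% of subjects injecting at home before the visit, the Week 4 and 8 share is about 10-12% if every postponed draw is on the earliest day, and 19-26% if it is 10-15 days after the dose.
- Week 14, visit SD 2, dose-day SD 1.2, with 10%, 30% or 50% injecting at home: 0.6%, 1.8% or 3.0% if drawn on the earliest day; 3%, 8% or 14% if drawn 10-15 days after the dose.

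The answer follows the assumed behaviour, so none of these figures is an estimate of the loss.

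**The case against.** **Week 14 is well protected.** This largely stands. All allowed visit days are inside the window, and so is Day 109. The protocol asks for postponed draws at the earliest possible time, wants visits placed on dose days where possible, has a dose due on a visit day held until the procedures are done, and allows a dose up to 4 days late, so the Day-99 dose can wait until the last allowed visit day (Day 102). Only an injection on Day 100 or 101 before a later in-window visit forces a draw past Day 109; otherwise the draw has to slip. A reader might infer that postponed Week 14 draws are lost as a class, but Step 4 shows they are not.

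**hs-CRP and special studies.** A reader might extend the point to hs-CRP. The documents do not support that. The 10-day rule covers the lipid panel with direct LDL-C, ADA, PK and PCSK9. The special studies (apo B, apo A-I, Lp(a), hs-CRP) are listed separately without it, and after randomization they are taken only at Weeks 14 and 52, so the Week 4 and 8 gaps cannot touch them.

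**The values are not thrown away.** This stands in part. LDL-C values remain eligible for the last-value ANCOVA, and a subject missing one visit still contributes to the MMRM through others. The sample is nonetheless missing from the by-visit analysis it was drawn for.

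**Narrow windows are a legitimate choice.** An author may prefer values close to the target, and the SAP deliberately uses different windows for safety. But ±10 days at Weeks 4 and 8 beside ±30 from Week 26 onward does not follow from wanting tight windows, and the SAP gives no reason for excluding allowed visit days.

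**Conclusion.** The mismatch is real and confined to a few visits. Table 3 is narrower than the protocol at Weeks 4 and 8 only. Samples drawn on Days 15-18, 40-46 and 68-71 enter neither the biomarker MMRM nor the by-visit LDL-C response summaries. At Week 14 the exposure is at the upper edge: a postponed lipid draw can fall on Day 110 or 111, or later if it slips.

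A reader might infer that Table 3 is too narrow throughout, or that the trial's main conclusion is at risk. Neither follows. Every later legible window is wider than its visit window, and the primary and other clinical endpoints do not use Table 3.

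The size of the loss cannot be estimated from the documents. My judgement is that it is probably small, given how the protocol steers visits and draws, and similar in both arms, since both follow the same blinded visit and dosing rules. Nothing in the documents points to a bias in the treatment comparison. The day counts rest only on the stated windows and day numbering; the percentages in the working rest on assumed timing. Label: cheap improvement.

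**What to change.** Widen Table 3 so that allowed lipid draws have a window, keeping the existing rule of using the value nearest the target. For example:

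- Week 4: Days 15-42.
- Week 8: Days 43-71. Day 43 is 14 days from both targets, so it has to be given to one of them; this places it in Week 8.
- Week 14: keep the lower limit at Day 89 and extend the upper limit a few days, for example to about Day 113, the next nominal dosing day. That takes in the Day 110-111 draws and a short slip after a Day-99 dose. Copying Table 4's Week 14 window (Days 78-140) is not necessary and would admit values 140 - 99 = 41 days late.

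These limits cover every allowed visit day. A draw postponed from the end of the Week 8 window could still be unassigned (injection Day 70, visit Day 71, draw no earlier than 70 + 10 = Day 80), so add one sentence on how between-window values are handled.

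The cost is a change of cut-points in one table and in the program that reads it. The downside is that a few values slightly further from the target day are used.

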### 9.1.1. Cognitive Testing Sample Size

One of the objectives for this trial is to describe the safety of bococizumab and placebo with respect to assessments of cognitive testing. Cognitive testing will be performed at baseline (Visit 5), annually, and at the EDC and EOS visits at a subset of designated study sites in approximately 500 subjects (250/treatment group). This number of subjects is based on feasibility of sites with the appropriate staff and workspace to administer the testing accurately.

Assuming 80% of the 500 subjects will have cognitive testing performed at Visit 11 (Week 52) and 70% at Visit 14 (Week 104), it is expected that 400 subjects (200/group) will have cognitive testing at Week 52 and 350 subjects (175/group) at Week 104. Precision estimates are defined as the half-width of the 95% confidence interval for these assumed sample sizes at Week 52 and Week 104 for each cognitive test and are displayed in the table below.

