2.1. Study Design

This is an event driven, Phase 3 multi-center, double-blind, randomized parallel group evaluation of the efficacy, safety, and tolerability of bococizumab compared with placebo, in reducing the occurrence of major cardiovascular (CV) events in subjects at risk, who are on background lipid lowering treatment and have an LDL-C \geq 70 mg/dL (1.81 mmol/L) or non-HDL-C \geq 100 mg/dL (2.59 mmol/L). After obtaining informed consent, there will be a pre-screening visit. At this visit subjects will have consented to have had lipid levels assessed and to provide medical records for review, only, so as to determine if the subject qualified for this study. If qualified, [t]he interactive response technologies (IRT) system will determine if the subject is eligible for the study or if the subject should be screen failed. This will be followed within 30 days, by a screening visit, and a run-in period of up to 6 weeks, during which subjects will be fully assessed with respect to the trial enrollment criteria and compliance with the self-administration of subcutaneous injections. The run-in period will be followed by the treatment period, the duration of which will be determined by the number of subjects with primary endpoint events, and concluded by a safety follow-up period, as illustrated in the schematic below (Figure 1).

Figure 1 B1481022 Study Diagram

The End of Study (EOS) will be announced to study sites, when the Sponsor estimates that criteria for stopping the study in Section 3 of the protocol have been satisfied. EOS visits should be scheduled as soon as possible, after that announcement. The EOS visit should occur no sooner than 14 days after the last dose of investigational product (IP) was administered for subjects taking IP. If the EOS visit has taken place earlier than 40 days after the last dose of IP administration, subjects will receive a telephone call to determine if any serious adverse events have taken place. All EOS procedures should be done for all randomized subjects when the study is completed, whether or not the subject is taking double-blind investigational product.

Approximately 85,000 subjects may be screened and approximately 17,000 subjects will be randomized. Subjects will be randomized to bococizumab 150 mg or placebo Q2wks in a 1:1 ratio. Randomization will be stratified by geographic region and LDL-C at the pre-screening visit (<100 mg/dL, ≥100 mg/dL).

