Hematology	Chemistry	Urinalysis***	Additional
Hemoglobin	BUN	pH	Serum pregnancy (WCBP)*
Hematocrit	Creatinine	Specific gravity	Urine pregnancy***
RBC count	Glucose	Bilirubin	(WCBP)*
Mean corpuscular volume (MCV)	Ca⁺⁺	Urobilinogen	
Mean corpuscular hemoglobin (MCH)	Na⁺, K⁺, Cl	Nitrite	Hepatitis panel**
Mean corpuscular hemoglobin concentration (MCHC)	Total CO2 (Bicarbonate)	Leukocytes	ADA*
Platelet count	Uric acid	Glucose (qual)	PCSK9*
WBC count	Albumin	Protein (qual)	bococizumab*
Total neutrophils (Abs)	Total protein	Blood (qual)	
Eosinophils (Abs)	LDH	Ketones	
Monocytes (Abs)	Magnesium	Urine albumin/creatinine ratio*	
Basophils (Abs)	Phosphorus		
Lymphocytes (Abs)	CK		
	CK-isozymes*		
	eGFR		
	HbA1c*		
	Liver function:		
	AST/ALT		
	Gamma-glutamyl transferase (GGT)*		
	Total bilirubin		
	Direct bilirubin		
	Indirect bilirubin		
	Alkaline phosphatase		
	Lipid profile (total cholesterol, LDL-C, non-HDL-C, HDL-C, RLP-C, VLDL-C, triglycerides)*		
	Special chemistry assessments (hs-CRP, Lp(a), Apo B, Apo A-I)*		

* Where applicable and according to the Schedule of Activities (SOA)

** Hepatitis B and C virus serologies at screening for all subjects and Hepatitis C virus serologies will be collected at EDC/EOS only for subjects from study sites in Canada. A positive or indeterminate hepatitis C serology may trigger a hepatitis C PCR test for confirmation.

*** Performed locally

Qual = qualitative; WCBP= women of childbearing potential; Abs=absolute.

Cognitive testing

Cognitive testing will be performed at baseline (Visit 5), annually, and at the EDC and/or EOS visits at a subset of designated North American study sites in approximately 500 subjects (250/treatment group). The cognitive testing battery will comprise the following assessments:

- Wechsler Adult Intelligence Scale (WAIS-III) – Digit Span (Forward and Backward).

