Observations of potential clinical concern after the first dose of study medication for hematology, blood chemistry and all urinalysis parameters will be tabulated by treatment group as categorical variables according to sponsor standards. Subjects meeting one or more criterion for Hy's Law will be tabulated by treatment group according to sponsor standards.

The maximum post-randomization total bilirubin value will be plotted against the maximum post-randomization alanine transaminase (ALT) value (Evaluation of Drug-Induced Serious Hepatotoxicity [eDISH] plot).

Electrocardiograms

12-lead ECGs will be locally read and the interpretations will be kept at the investigation sites as source documents. Any clinically significant ECG abnormalities will be reported as AEs. As a result of the discontinuation of the bococizumab clinical development program, ECG data will not be summarized or listed.

Physical and neurological exams

As a result of the discontinuation of the bococizumab clinical development program, physical examination findings will not be listed. Also, neurological exam findings will not be summarized or listed.

Cognitive Tests

Changes from baseline in cognitive test results, including the Digit Span Forward score, Digit Span Backward Score, Digit Symbol - Coding score, Trail Making A score, Trail Making B score, HVLT Total Recall score, HVLT Delayed Recall Trial score, and HVLT Recognition score will be analyzed using an MMRM model. The fixed effects will be treatment group (categorical variable), scheduled visit time point (categorical variable), baseline value (continuous variable), interaction between baseline value and scheduled visit time point and interaction between treatment and scheduled visit time point. REML

estimation will be used and the default covariance structure will be unstructured. Due to the slow onset of accrual in this event-driven trial, there will be few observations at the last several time points. One or more of the last visits may be removed to ensure convergence of the model fitting. If the model fitting fails to converge, compound symmetry will be used as the covariance structure. Consistent with MMRM model fitting, no explicit imputation of missing assessments will be performed. Estimates of treatment group means and mean treatment group differences at each visit along with corresponding 95% confidence intervals will be provided. The confidence intervals are for estimation purposes only.

Depression assessment

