16. Lipid profile: The fasting lipid profile includes total cholesterol, high density lipoprotein cholesterol (HDL-C), low density lipoprotein cholesterol (LDL-C), very low density lipoprotein cholesterol (VLDL-C), remnant lipoprotein cholesterol (RLP-C), and triglycerides, performed by a central laboratory. After randomization lipid level tests should be scheduled no sooner than 10 days after the subject's prior dose, even if this requires an unscheduled visit. If a subject has a visit that is scheduled less than 10 days after the last dose, the visit procedures may take place, but lipid testing should be postponed and performed at the earliest possible time, at an unscheduled visit, no sooner than 10 days after the subject's last dose. Subjects who have had an IP dose frequency modification to dosing every 4 weeks, will need to have their visit frequency increased to every 8 weeks, approximately, for the purposes of direct LDL-C measurement. A lipid profile will not be collected at EDC/EOS visits.
17. Special Lipid and Efficacy Assessments: At the screening visit hs-CRP and Lp(a) assessment may be evaluated, in subjects who have had a cardiovascular event more than 5 years prior to screening and in subjects without a prior qualifying cardiovascular event. Apolipoprotein (apo) B and apo A-I will not be collected at the screening visit. Special lipid and efficacy blood samples will be collected in all subjects, at Visits 5, 8, and 11, for apo B, apo A-I, Lp(a), and hs-CRP, as described in Section 6, and measured by a central laboratory.
18. HbA1c: HbA1c will be collected, for all subjects, at baseline, Visit 11, and EDC or EOS. HbA1c may be collected at any time, at an unscheduled visit, if necessary for additional safety assessments, as determined by the investigator.
19. Viral hepatitis serologies. Hepatitis B and hepatitis C virus screening serologies will be collected at Visit 1 in all subjects and evaluated as per Appendix 3. Hepatitis C virus serologies will be collected at the EDC/EOS visit only for subjects from study sites in Canada. A positive or indeterminate hepatitis C serology may trigger a hepatitis C polymerase chain reaction (PCR) test for confirmation. Unscheduled visits for hepatitis C PCR testing do not require fasting.

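### SAP Table 4 sorts annual cognitive tests into 15 full-calendar windows, so most EOS tests fall at visits with no scheduled test and the default unstructured MMRM is not realistically estimable

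*SAP*

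**What the plan says.** SAP 6.2 sets the schedule: "Cognitive testing will be performed at baseline (Visit 5), annually, and at the EDC and/or EOS visits". Appendix 2 adds that there are "EDC/EOS visits, which will not have visit windows", and SAP 2.1 that "All EOS procedures should be done for all randomized subjects when the study is completed". An EDC or EOS test can therefore fall on any study day.

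SAP Appendix 1.1 says that the cognitive MMRM needs observations assigned to scheduled visits. It supplies Table 4, whose title names cognitive assessments. The table has 15 windows (Visits 6 to 20) and no EDC/EOS category, and "The safety windows will touch, so that all post-baseline safety observations will fall in a window".

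SAP 8.2.3 fits visit as a category, with treatment-by-visit and baseline-by-visit terms and an unstructured covariance by default. If fitting is difficult, "One or more of the last visits may be removed to ensure convergence of the model fitting"; after that comes compound symmetry. The cognitive model has no spatial-power step, unlike the biomarker model in SAP 8.2.2.

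For HbA1c, Appendix 2 footnote 18 says "HbA1c will be collected, for all subjects, at baseline, Visit 11, and EDC or EOS". SAP 8.2.3 tabulates it by visit, plots mean changes and gives shift tables. It is not modelled.

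Protocol 9.1.1 sized the cognitive sub-study for two visits: "it is expected that 400 subjects (200/group) will have cognitive testing at Week 52 and 350 subjects (175/group) at Week 104".

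**The concern.** The windows follow the clinic calendar, not the test calendar. An EOS battery on Day 491 becomes a Week 70 cognitive result, although none is scheduled then. The estimates at Weeks 4 to 40, 70, 86, 122 and 140 would consist only of subjects who had stopped treatment early or whose study had ended. Printed in visit order, they would look like a time course.

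Two non-annual windows can both be filled in one subject only if that subject had both an EDC and an EOS test. Many covariances therefore have little or no data behind them. The SAP's convergence remedy expects sparse data at the last time points, whereas here the sparse windows lie before and between the annual visits.

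At stake are the readability of the cognitive safety results, the covariance structure actually used, and the number of subjects contributing at Weeks 52 and 104.

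**Working it through.** **1. The plan's own precision figures.** Protocol Table 3 uses 1.96 × SD × √(2/n).
- Digit Symbol, SD 9: n = 200 gives 1.76 and n = 175 gives 1.89, as stated.
- Digit Span 0.39/0.42, Trail A 4.31/4.61, Trail B 7.84/8.38 and HVLT Learning 0.78/0.84 also reproduce.

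**2. Share of Table 4 that holds a scheduled test.**
- The Week 52 window is Days 323–427 (105 days), Week 104 is Days 666–791 (126) and Week 156 is Days 1037–1155 (119). The sum is 350 of the 1,399 days from Day 2 to Day 1400, or 25%. The other 1,049 days (75%) lie in windows with no scheduled cognitive test.
- The Visit 16 row is not legible in the public copy. Because the windows touch, it must be Days 918–1036.
- Scheduled cognitive tests occupy 4 of 15 windows and scheduled HbA1c 1 of 15.
- These are shares of calendar days, not of tests.

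**3. Share of EOS tests off schedule.** Assumptions: accrual as in Protocol 9.1 (3.1 years, half in the last ten months), stop at the end of accrual, EOS 14 to 60 days later, no dropout.

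| Where the EOS test falls | Share |
|---|---|
| Window with no scheduled cognitive test | 77% |
| Week 52 window | 8% |
| Week 104 window | 8% |
| Week 156 window | 7% |

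Uniform accrual over 2 to 3.1 years gives 69% to 75% off schedule. A separate simulation of 500 subjects added EDC tests (assumed rate 5% to 20% per year, maximum follow-up 730 to 1,150 days) and gave 68% to 78% of EDC/EOS tests. Under the planned 4.8-year duration the share would have been 48% to 55%.

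**4. Covariance.** An unstructured matrix for k visits has k(k+1)/2 parameters.
- k = 15 gives 120. From the original protocol (26 August 2013) to the stop (01 November 2016) is 1,163 days, and the Visit 19 window opens on Day 1282. At most 13 windows should therefore be filled, giving 91 parameters.
- In the early-stop simulations 9 to 13 windows were filled, making 36 to 78 visit pairs. Between 3 and 38 of those pairs were never seen together in any subject, and most pairs were seen in fewer than 5 subjects.
- Across all 24 scenarios (early stop and planned duration), compound symmetry had a full-rank design and converged in 19. The other 5, all at the 5% EDC rate, had at least one treatment-by-window cell with no observation.

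**5. What annual windows would add.** Same assumptions as step 3. A subject contributes at Week 52 under Table 4 if EOS is on or after Day 323, and under annual windows from Day 183 if EOS is on or after Day 183. For Week 104 the cut-offs are Day 666 and Day 547. The n per arm is the share × 250, and the half-width uses the step 1 formula with SD 9.

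| Visit | Table 4 | Annual windows |
|---|---|---|
| Week 52, share contributing | 53% | 76% |
| n per arm, half-width | 133, ±2.16 | 190, ±1.81 |
| Week 104, share contributing | 30% | 38% |
| n per arm, half-width | 76, ±2.86 | 94, ±2.57 |

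The half-widths are unadjusted and only illustrate scale. About 24% of EOS tests fall before Day 183.

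**The case against.** **The model can be fitted.** A reader might infer that no planned model can be fitted. The documents do not support that: the plan is a sequence ending in compound symmetry, which usually fits. What stands is that the default structure is not a realistic option, and that empty cells can leave some contrasts non-estimable even under compound symmetry.

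**Weeks 52 and 104 are not emptied by the windows.** A reader might also infer that Table 4 drains these visits. It does not: scheduled tests (±3 and ±14 days) fall well inside their windows. Most of the shortfall against the protocol's 200 and 175 per group comes from the early stop. What stands is that nearby EOS tests are sent elsewhere.

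**HbA1c.** It would be wrong to say that rows other than Week 52 hold only EDC/EOS samples, because footnote 18 also allows unscheduled samples. The shifts to the smallest and largest post-baseline values do not depend on windows.

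**Scheduled visit could mean annual visits only.** On that reading off-schedule tests would simply drop out. The SAP does not say so, and its statement that all observations fall in a window points the other way.

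**Low stakes.** SAP 8.2.3 calls the safety summaries descriptive and says the cognitive intervals are for estimation only. This stands in full.

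**Conclusion.** The mismatch is in a written rule and should be corrected, but its reach is limited. Under the stop that occurred, roughly 70% to 78% of EOS cognitive tests would be labelled as visits with no scheduled test. The range rests on assumed accrual, since the documents give none for the roughly 500 North American subjects; the lowest value in any early-stop case was 68%. The default unstructured MMRM could not realistically be estimated, removing last visits does not help, and compound symmetry would probably be used, with sparse or missing contrasts at some visits. The avoidable loss at the sized visits is about 23 percentage points of subjects at Week 52 (53% against 76%) and about 8 at Week 104 (30% against 38%). For HbA1c only the reading of by-visit rows is affected. No hypothesis test, alpha allocation or efficacy conclusion is touched.

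**What to change.** Give the cognitive MMRM its own touching windows, split at the midpoints of the annual targets (Days 365, 729, 1093 and 1457):
- Week 52: to Day 546, with a stated lower bound such as Day 183
- Week 104: Days 547–910
- Week 156: Days 911–1274
- Week 208: from Day 1275

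The unstructured matrix then has 4 × 5 / 2 = 10 parameters, or 6 if Week 208 is empty.

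Report tests before the lower bound, and any EDC/EOS test displaced by the closest-to-target rule, in a last-post-baseline-value summary by arm. Disclose that about 24% of EOS tests would fall before Day 183 under the assumptions above. Tabulate HbA1c at Week 52 and at the last post-baseline value.

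The cost is one window table and one summary in the SAP, a wider spread of days within each annual visit, and the removal of the earliest EDC/EOS tests from the MMRM. For many recently randomized subjects that is the only post-baseline test, which is why the last-value summary is needed.
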